Randomization will be accomplished using randomizer.org software to generate a set of 90 numbers from 1 to 3 for 90 enrolled participants. Each digit from 1 to 3 will correspond to a study arm.

Data Acquisition

Study data will be acquired through the means of the aforementioned questionnaires (Questionnaires, see Appendix VI), phone interviews, and by simple chart review. The secondary outcome of "cost of visit" will be acquired through Medical Records.

Institution/Hospital: Vanderbilt Children's Hospital

VIII. Predictor Variables

Predictor variables are the 3 treatment allocation arms: Dermabond[™], Steri-Strips[™], and absorbable sutures. Other independent variables to be collected include demographics of the patient (age, sex, race/ethnicity), specifics of the laceration (location, length and width, time between trauma and wound closure) and level of training of the provider who will be closing the wound. Demographics will be extracted from the patient Electronic Medical Record and from the parent Questionnaire (Questionnaires, see Appendix VI). Both the specifics of the laceration and the level of training of the provider will be extracted from the provider questionnaire at the time of the procedure (Questionnaires, see Appendix VI).

IX. Outcome Variables

a. Primary outcome variable

The primary outcome will be cosmesis of the resultant scar as measured on a 100 mm Visual Analogue Scale where a score of 0 corresponds to "worst scar" and a score of 100 corresponds to "best scar." This scale has been validated as a scoring method to evaluate cosmesis of a scar. 12, 16, 17, 23, 32 Due to its sensitivity and the fact that it provides parametric data, the scale allows for smaller, more practical sample sizes to show clinically-significant differences in populations. 12, 16, 17, 23, 32 The Visual Analogue Scale will be used by two Plastic Surgeons blinded to closure method to rate a patient's scar at 3 months. In addition, parents will be asked to rate the scar on a scale of 0 to 100 during their over-the-phone interview at 3 months. We will compare their rating of their child's scar to the average of their ratings of the 3 images of random scars at the initial visit.

b. Secondary outcome variables

i. Pain experienced by patient

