Patients and their parent/guardian(s) will be told very explicitly by the investigators that their participation in this research investigation is entirely voluntary and that they may withdraw at any time. We will further emphasize verbally and in the informed consent document that a decision on the part of the patient or parent/guardian(s) to not participate will in no way change, compromise or jeopardize the patient's care. Indeed, we anticipate that a number of eligible patients will not be enrolled on this basis.

XIV. Data Management

Participants' information (Subject Enrollment Form, see Appendix II, Questionnaires, see Appendix VI, pictures) will be kept in a separate file for each subject. Data will be transferred to the REDCap® server. This data will then be sent for statistical analysis.

XV. Statistical Considerations

We are planning a study of a continuous response variable from independent control and experimental subjects with 1 control per experimental subject. In previous studies, the response within each subject group was normally distributed with a standard deviation of 15 mm on a 100 mm Visual Analogue Scale and the minimal clinically important difference between two scars was 15 mm on a 100 mm Visual Analogue Scale. We performed multiple sample size power calculations using STATA® 14.1 (College Station, Texas). Using one-way ANOVA, with a power of 90% and an alpha of 0.05, we would need between 5 and 21 subjects per group to detect a clinically significant difference of 5 to 15 mm between groups depending on the standard deviation in each group (in anticipation of the fact that we may have a larger standard deviation). In order to assure an effective sample size after accounting for dropouts and missing data, we propose to recruit 30 experimental subject per treatment arm and 30 control subjects, for a total of 90 subjects.

XVI. Privacy and Confidentiality Issues

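### The power statement's 5 to 21 per group for 5 to 15 mm cannot be reproduced; at the one SD cited (15 mm), a largest difference of 5 mm needs at least 172 per group

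*Combined protocol and SAP*

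**What the plan says.** All of the relevant text is one paragraph, Section XV (Statistical Considerations).

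- It reports from previous studies that "the response within each subject group was normally distributed with a standard deviation of 15 mm" and that "the minimal clinically important difference between two scars was 15 mm on a 100 mm Visual Analogue Scale".
- It then gives the calculation: "Using one-way ANOVA, with a power of 90% and an alpha of 0.05", the authors say "we would need between 5 and 21 subjects per group to detect a clinically significant difference of 5 to 15 mm between groups".
- It qualifies the range as "depending on the standard deviation in each group", and says the SD was varied "in anticipation of the fact that we may have a larger standard deviation".
- It proposes 30 per arm, 90 in total, to cover dropouts and missing data. No dropout rate is given.

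No other section supplies an SD, a set of means or a pairing of n with difference.

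**The concern.** A one-way ANOVA sample size needs three inputs besides alpha and power: the within-group SD, the three means, and the n that follows from them. The paragraph gives one SD and no means, and it runs a range of n alongside a range of differences without linking them. A reader cannot check it.

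The natural reading is also hard to believe. Detecting 5 mm against an SD of 15 mm means detecting a third of an SD, which cannot be done with 21 per group or fewer. An SD above 15 mm would raise the requirement further.

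This is the plan's only power statement. Section I hypothesises equivalent cosmetic outcomes, and Section II expects no clinically significant difference. Someone who believes the trial had 90% power for 5 mm could take a non-significant ANOVA as ruling out differences of that size.

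**Working it through.** **Inputs from Section XV.** Three groups, alpha 0.05, power 90%, SD 15 mm, differences of 5 to 15 mm, 5 to 21 per group, 30 per arm recruited.

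**Assumptions.** The plan states no means, so I used three main patterns for a difference d:

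- A, one arm differs: 0, 0, d
- B, evenly spread: 0, d/2, d
- C, d is the step between neighbouring arms: 0, d, 2d (largest difference 2d)

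For a fixed largest difference, A is the most favourable pattern and B the least.

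**Formula.** Power = P[F′(2, 3(n−1), λ) > F₀.₉₅(2, 3(n−1))], where F′ is noncentral F and λ = n·Σ(mᵢ − m̄)²/SD². The sum of squares is 2d²/3 for A, d²/2 for B and 2d² for C.

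**The plan's upper figure, 21.** Take 15 mm, SD 15, pattern A. Then λ = 21 × 150/225 = 14.0, with df 2 and 60, and power is 0.915. With 20 per group it is 0.8997. So 21 is exactly the requirement for 15 mm at SD 15 if one arm differs. Pattern B needs 27.

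**The 5 mm end at SD 15.** For pattern A the sum of squares is 2 × 25/3 = 16.67. With n = 171, λ = 171 × 16.67/225 = 12.67 and power is 0.8985. With n = 172, λ = 12.74 and power is 0.9003. The requirement is therefore 172.

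Number needed per group at SD 15, 90% power:

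| d | A | B | C |
|---|---|---|---|
| 5 mm | 172 | 229 | 58 |
| 10 mm | 44 | 58 | 16 |
| 15 mm | 21 | 27 | 8 |

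Power for d = 5 mm at SD 15:

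| n per group | A | B | C |
|---|---|---|---|
| 21 | 18% | 14% | 46% |
| 30 | 24% | 19% | 62% |

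**What SD would each stated figure require?** Section XV says the SD varied, so I solved for the largest SD that still gives 90% power:

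| Case | A | B | C |
|---|---|---|---|
| 5 mm, n = 21 | 5.1 | 4.4 | 8.9 |
| 15 mm, n = 5 | 6.7 | 5.8 | 11.7 |
| 15 mm, n = 21 | 15.4 | 13.3 | 26.6 |
| 15 mm, n = 30 | 18.5 | 16.0 | 32.1 |

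Every SD in the first two rows is below 15 mm, whereas the text says the SD was varied in case it proved larger. In the third row, 21 per group leaves essentially no room above 15 mm when 15 mm is the largest difference (A and B). Room appears only if the largest difference exceeds 15 mm.

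**Smallest largest-difference with 90% power at SD 15 (A / B).** 33.4 / 38.5 mm with 5 per group, 14.6 / 16.9 mm with 21, and 12.1 / 14.0 mm with 30. The last pair is 2.4 to 2.8 times 5 mm (12.1/5 and 14.0/5).

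**The planned size at 15 mm, SD 15 (A / B).** 98% / 94% with 30 evaluable per arm, 97% / 91% with 27 (an assumed 10% loss), and 91% / 81% with 21.

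**Equal arms.** The Randomization paragraph of Section VII will "generate a set of 90 numbers from 1 to 3 for 90 enrolled participants" and mentions no balancing. If the allocations are drawn without balancing, average power for 15 mm at SD 15 with 90 evaluable is 0.979 / 0.931, against 0.982 / 0.936 with equal arms (3,000 simulated allocations). The equal-arm assumption changes little.

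**The case against.** The strongest reply is that no arithmetic error is proven. Section XV says n depends on the SD and never says that 15 mm was used at the 5 mm end, so 172 is conditional on an SD and a reading that the plan does not tie to that n. This stands: the calculation actually run is unknown.

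A scenario also exists that gives the stated range. If 5 and 15 mm are the two gaps within one set of means, 0, 5, 20, then 5 per group suffices up to an SD of 8.1 mm and 21 per group up to 18.5 mm. At SD 15 it needs 15 per group. This pattern would fit the remark about a larger SD at the upper end. But its largest difference is 20 mm, which the plan does not state, and its low end still needs an SD well below 15 mm. On this reading the paragraph gives no 90% power for a 5 mm difference at all. The nearby pattern 0, 5, 15 needs 26 per group at SD 15, outside the range.

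A third point is that the practical effect is limited, because 30 per arm is ample for 15 mm at SD 15. That is right for an ANOVA aimed at detecting a difference. It says nothing about power to show equivalence, which is a separate question not assessed here.

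**Conclusion.** The concern holds. The stated range cannot be reproduced from the plan, and its 5 mm end conflicts with the only SD given. At SD 15 mm, 90% power for a largest difference of 5 mm needs at least 172 per group, about eight times the stated maximum of 21 (172/21 = 8.2). The most generous of the three main patterns, with 5 mm as the step between arms, still needs 58. The 5-per-group end requires an SD below 15 mm on every pattern examined. Calling 5 mm clinically significant contradicts the 15 mm minimal clinically important difference in the same paragraph, and that needs no calculation.

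The figures rest on a balanced three-group ANOVA, on SD 15, and on mean patterns that I assumed. They do not show that 90 is too few for an ANOVA at 15 mm. The fault lies in what the power statement claims and leaves out, and it should be corrected.

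**What to change.** In Section XV, delete the claim of 90% power for 5 mm, unless the original inputs are stated and support it. Give the SD, the three means and the n for each figure, and state the assumed loss to follow-up. Keep the remark about a larger SD only if a stated scenario supports it. If the calculation used other means, such as 0, 5, 20, report those means and their SDs instead. Otherwise, text such as this would serve:

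> At SD 15 mm, the three-group ANOVA (alpha 0.05) has 91%, 97% and 98% power for a largest difference of 15 mm with 21, 27 and 30 evaluable per arm if one arm differs (81%, 91% and 94% if the means are evenly spread). With 30 per arm the smallest largest-difference with 90% power is 12.1 mm (14.0 mm if evenly spread), and 90% power for 15 mm holds up to an SD of 18.5 mm (16.0 mm). At SD 20 mm, power for 15 mm with 30 per arm is 85% (73%). Equal evaluable numbers per arm are assumed.

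The cost is a text correction in one section and a less favourable stated power. The total of 90, the procedures, the endpoint and the analysis do not change.
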